- Duration of objective response (DOR) is defined as the time from the first occurrence of a documented objective response to the time of progression, as determined by the Investigator using RECIST, v1.1 (except for prostate cancer and malignant pleural mesothelioma) and disease-specific criteria for patients with prostate cancer (see [Appendix 6](#)) and malignant pleural mesothelioma (see [Appendix 7](#)), or death from any cause, whichever occurs first. For patients who do not die or experience disease progression before the end of the study or who are lost to follow-up, duration of objective response will be censored at the day of the last tumor assessment
- Progression-free survival (PFS) is defined as the time from the first day of study treatment to the first occurrence of disease progression, as determined by the Investigator using RECIST, v1.1 (except for prostate cancer and malignant pleural mesothelioma) and disease-specific criteria for patients with prostate cancer (see [Appendix 6](#)) and malignant pleural mesothelioma (see [Appendix 7](#)), or death from any cause, whichever occurs first. A patient without a PFS event will be censored at the time of the last evaluable tumor assessment. Patients with no tumor assessment after the baseline visit will be censored at the time of the first day of study treatment plus 1 day

- Time to progression (TTP) is defined as time from the first day of study treatment to the first occurrence of progressive disease, as determined by the Investigator using RECIST, v1.1 (except for prostate cancer and malignant pleural mesothelioma) and disease-specific criteria for patients with prostate cancer (see [Appendix 6](#)) and malignant pleural mesothelioma (see [Appendix 7](#)), or death due to reason of disease progression, whichever occurs first. Patients who have not progressed or died due to disease progression at the time of study completion or who are lost to follow-up will be censored at the date of the last evaluable tumor assessment. Patients with no tumor assessment after the baseline visit will be censored at the time of the first day of study treatment plus 1 day
- Overall survival (OS) is defined as the time from the first day of study treatment to death from any cause. Patients for whom no death is captured on the clinical database will be censored at the most recent date they were known to be alive

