Appendix 1 Schedule of Assessments

	Screening ¹	Treatment (All cycles, unless otherwise indicated) ²	Treatment discontinuation visit	Follow-Up	End of Study Visit
Day (Window)	Days -35 to -1	Day 1 (\pm 3 days for cycles \geq 2)	\leq 30 days after last dose	Every 3 months from study treatment discontinuation (\pm 30 days)	24 months
Informed consent ¹	X				
Review of eligibility criteria	X				
Medical history and demographics ³	X				
Cancer history ⁴	X				
Concomitant medications ⁵	X	X	X		
Tumor assessment RECIST 1.1 and modified RECIST per Appendix 3⁶	X	Every 6 weeks, \pm 5 days (2 cycles) for the first 24 weeks and every 12 weeks, \pm 5 days (4 cycles) thereafter until loss of clinical benefit, withdrawal of consent, death, or study termination by the Sponsor, whichever occurs first			
Brain MRI/CT Scan with contrast ⁶	X				
Specific tumor markers ⁷	X	As clinically indicated, but at least every 6 weeks, \pm 5 days (2 cycles) for the first 24 weeks and every 12 weeks, \pm 5 days (4 cycles) thereafter until loss of clinical benefit, withdrawal of consent, death, or study termination by the Sponsor, whichever occurs first			
Collection of results from specific markers assessed on tumor tissue ⁸	X				

Appendix 1

Schedule of Assessments (cont.)

	Screening ¹	Treatment (All cycles, unless otherwise indicated) ²	Treatment discontinuation visit	Follow-Up	End of Study Visit
Day (Window)	Days –35 to –1	Day 1 (\pm 3 days for cycles \geq 2)	\leq 30 days after last dose	Every 3 months from study treatment discontinuation (+/- 30 days)	24 months
Physical examination ⁹	X	X	X		
ECOG performance status	X	X(-3 days from treatment start)	X		
Vital signs ¹⁰	X	X	X		
Oxygen saturation (pulse oximetry)	X	X	X		
12-lead electrocardiogram ¹¹	X	X	X		
Weight	X				
Height	X				

Appendix 1

Schedule of Assessments (cont.)

	Screening ¹	Treatment (All cycles, unless otherwise indicated) ²	Treatment discontinuation visit	Follow-Up	End of Study Visit
Day (Window)	Days -35 to -1	Day 1 (\pm 3 days for cycles \geq 2)	\leq 30 days after last dose	Every 3 months from study treatment discontinuation (+/- 30 days)	24 months
Local laboratory assessments					
Hematology ^{12, 13}	X	X	X		
Serum chemistry ¹³	X	X	X		
Coagulation panel (aPTT, INR)	X		X		
C-reactive protein	X	X	X		
Urinalysis ¹⁴	X	X ¹⁵	X		
Serum pregnancy test ¹⁶	X				
TSH, free T3, free T4	X	Every 3 rd cycle (starting at C3, C6, C9 ctd.)	X		
HIV, HBV and HCV serology ¹⁷	X				

Appendix 1

Schedule of Assessments (cont.)

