New lesions alone do not qualify as progressive disease. However, their contribution to total tumor burden is included in the sum of the diameters, which is used to determine the overall modified RECIST tumor response.

EVALUATION OF BEST OVERALL RESPONSE USING MODIFIED RECIST

TIMEPOINT RESPONSE

It is assumed that at each protocol-specified timepoint, a response assessment occurs. **Table 1** provides a summary of the overall response status calculation at each timepoint for patients who have measurable disease at baseline.

MISSING ASSESSMENTS AND NOT EVALUABLE DESIGNATION

When no imaging/measurement is done at all at a particular timepoint, the patient is not evaluable (NE) at that timepoint. If only a subset of lesion measurements are made at an assessment, usually the case is also considered NE at that timepoint, unless a convincing argument can be made that the contribution of the individual missing lesion(s) would not change the assigned time point response. This would be most likely to happen in the case of PD. For example, if a patient had a baseline sum of 50 mm with three measured lesions and at follow-up only two lesions were assessed but those gave a sum of 80 mm, the patient will have achieved PD status, regardless of the contribution of the missing lesion.

Appendix 3

Modified Response Evaluation Criteria in Solid Tumors (cont.)

Table 1 Modified RECIST Timepoint Response Definitions

% Change in Sum of the Diameters (Including Measurable New Lesions When Present)	Target Lesion Definition	Non-Target Lesion Definition	New Measurable Lesions	New Unmeasurable Lesions	Overall Modified RECIST Timepoint Response
– 100% ^a	CR	CR	No	No	CR
– 100% ^a	CR	Non-CR or not all evaluated	No	No	PR
≤ – 30%	PR	Any	Yes or no	Yes or no	PR
> – 30% to < + 20%	SD	Any	Yes or no	Yes or no	SD
Not all evaluated	Not evaluated	Any	Yes or no	Yes or no	NE
≥ + 20%	PD	Any	Yes or no	Yes or no	PD

CR = complete response; NE = not evaluable; PD = progressive disease; PR = partial response; RECIST = Response Evaluation Criteria in Solid Tumors; SD = stable disease.

^a When lymph nodes are included as target lesions, the % change in the sum of the diameters may not be 100% even if complete response criteria are met since a normal lymph node is defined as having a short axis of < 10 mm. Any pathological lymph nodes (whether target or non-target) must have reduction in short axis to < 10 mm in order to meet the definition of CR.

BEST OVERALL RESPONSE: ALL TIMEPOINTS

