4. PD, for a patient with an overall tumour response assessment of PD at any visit, and does not meet the criteria for a BOR of CR, PR or SD.
5. Missing, for a patient with an assessment of SD, PR or CR in the first 42 days after start of study treatment and no further tumour assessments thereafter.

Best overall response will summarize the proportion of patients with each best overall response.

Overall response rate (ORR) is defined as the proportion of patients with a BOR of CR or PR.

Clinical benefit rate (CBR) is defined as the proportion of patients with a BOR of CR, PR or SD.

Duration of response (DOR), based on RECIST v1.1, is defined as the time from the first occurrence of a documented objective response (CR or PR) to the time of progression or death from any cause, whichever occurs first. For patients who do not die or experience disease progression before the end of the study or who are lost to follow-up, duration of objective response will be censored at the day of the last tumor

assessment. Note: DOR will not be analysed if there are less than 4 patients available for the analysis.

Progression-free survival (PFS), based on RECIST v1.1, is defined as the time from the first day of study treatment to the first occurrence of disease progression or death from any cause, whichever occurs first. A patient without a PFS event will be censored at the time of the last evaluable tumor assessment or, for patients with no tumor assessment after the baseline visit, at the time of the first day of study treatment plus 1 day.

Time to progression (TTP), based on RECIST v1.1, is defined as time from the first day of study treatment to the first occurrence of progressive disease or death due to disease progression, whichever occurs first. Patients who have not progressed or died due to disease progression at the time of study completion or who are lost to follow-up will be censored at the date of the last evaluable tumor assessment or, for patients with no tumor assessment after the baseline visit, at the time of the first day of study treatment plus 1 day.

Overall survival (OS) is defined as the time from the first day of study treatment to death from any cause. Patients who are still alive at the time of analysis (clinical cut-off) and patients who are lost to follow-up will be censored at the last date they were known to be alive.

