4.9 MISSING DATA

Missing data in the non-progression rate, for the eligible-and-evaluable efficacy analyses, will be minimized by extending recruitment to allow for patients who do not meet the definitions of eligible and evaluable. Further imputation rules are described in section 4.4.1 for NPR at Week 18 and section 4.4.3 for NPR at Week 24.

Time to event endpoints will implement the censoring rules described in Section 4.4.3.

For the flagging of an adverse event or concomitant medication with partial start and/or end date as being on treatment: the missing date is not imputed per se but it is calculated whether the event or medication could *possibly* have started or been taken while on treatment, in which case it is taken as such.

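### DOR is censored at the last tumor assessment but PFS and TTP at the last evaluable one; the unexplained one-word difference can slightly lengthen censored response durations

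*SAP*

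**What the plan says.** SAP 4.4.3 defines three endpoints based on tumor assessments, with two censoring dates:

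- DOR: "duration of objective response will be censored at the day of the last tumor" assessment.
- PFS: "A patient without a PFS event will be censored at the time of the last evaluable tumor assessment".
- TTP: patients without an event "will be censored at the date of the last evaluable tumor assessment".

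Protocol 3.4.1 makes the same distinction. Its DOR rule reads "duration of objective response will be censored at the day of the last tumor assessment", while its PFS and TTP rules require an evaluable assessment. The synopsis repeats this. The SAP section on missing data adds no separate rule: "Time to event endpoints will implement the censoring rules described in Section 4.4.3".

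The Protocol foresees scans that are performed but not evaluable. Appendix 3, on missing assessments, states: "If only a subset of lesion measurements are made at an assessment, usually the case is also considered NE at that timepoint".

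Under the Protocol's Schedule of Assessments, scans take place every 6 weeks "for the first 24 weeks and every 12 weeks" thereafter, each with a window of 5 days either side. SAP 4.4.3 analyses DOR only if at least 4 patients are available. SAP 4.4.4.3 presents DOR by Kaplan-Meier, with a median and rates at 24 weeks, 6 months and 12 months.

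**The concern.** For a responder, DOR and PFS end on the same events: progression or death from any cause. Only the starting point differs. Apart from day-counting conventions, time from first dose to first response plus DOR should therefore equal PFS, whether the patient has an event or is censored. Two censoring dates break this identity for a censored responder whose last performed scan was not evaluable. The documents give no reason for the difference.

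The literal DOR rule can only lengthen a censored duration, never shorten it. The patient stays in the risk set over an interval that ends at an incomplete scan. If another responder has an event in that interval, the Kaplan-Meier step is smaller than it should be. With as few as 4 responders, one such patient can visibly change part of a curve. The programmer must also decide which date to use, and the text does not settle it.

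**Working it through.** The plan states no figure for DOR (no event count, power or target), so there is nothing to reproduce. The check compares the texts and then sizes the effect.

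**1. Extra time per affected patient.** The added time is the last performed scan date minus the last evaluable scan date. For one not-evaluable final scan this is one interval:
- up to Week 24: 6 × 7 = 42 days;
- after Week 24: 12 × 7 = 84 days, or up to 84 + 5 + 5 = 94 days with both windows.

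Several consecutive not-evaluable scans would add more.

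**2. Worked example with 4 responders** (illustrative, in weeks since first response). Events occur at 12, 30 and 48. One patient is censored, with the last evaluable scan at 24 and a not-evaluable scan at 36.

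| Step | Censored at 24 (evaluable) | Censored at 36 (literal) |
|---|---|---|
| Week 12, 4 at risk | 3/4 = 0.750 | 3/4 = 0.750 |
| Week 30 | 2 at risk: 0.750 × 1/2 = 0.375 | 3 at risk: 0.750 × 2/3 = 0.500 |
| Week 48, 1 at risk | 0 | 0 |

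The curves differ only between weeks 30 and 48. At the planned landmarks they agree: 75% at 24 weeks and at 6 months (about 26 weeks), and 0% at 12 months (about 52 weeks). The median is 30 weeks under both rules if it is the first time at which the estimate is 0.5 or less. Software that takes the midpoint when the curve sits at exactly 0.5 would give (30 + 48)/2 = 39 weeks under the literal rule.

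**3. Average effect by simulation.** All rates of not-evaluable scans are assumptions.

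*Simulation A*: 4 to 8 responders, exponential DOR with median 52 weeks, uniform censoring at 12 to 104 weeks, 10% to 30% of final scans not evaluable with a 12-week shift, 4,000 runs per setting. The literal rule raises the 52-week estimate by 0.4 to 1.4 percentage points.

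*Simulation B*: the Protocol's scan schedule; first response at week 6, 12 or 18; exponential DOR with median 30 weeks, or 77.6 weeks (the median DOR that Protocol 1.2.4.1 reports from another study of the drug); last contact uniform between weeks 30 and 120; each scan independently not evaluable at the rate shown; 3,000 runs per setting. The entries are the mean rise in 52-week Kaplan-Meier DOR, in percentage points:

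| Responders | Median DOR (weeks) | 0% | 5% | 10% | 20% |
|---|---|---|---|---|---|
| 4 | 30 | 0 | 0.3 | 0.6 | 1.3 |
| 4 | 77.6 | 0 | 0.2 | 0.4 | 1.0 |
| 8 | 30 | 0 | 0.3 | 0.6 | 1.4 |
| 8 | 77.6 | 0 | 0.2 | 0.4 | 1.0 |

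At rates of 5% to 20%, the mean extra time is 0.3 to 2.0 weeks per responder. The 52-week estimate changes at all in 1.3% to 7.5% of 4-responder cohorts and in 5.9% to 26.4% of 8-responder cohorts. The median changes in 0.2% to 3.6% of cohorts.

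**The case against.** The strongest reply is that this is drafting shorthand, not a second rule. No text says that a not-evaluable scan counts for DOR; that reading rests on one absent word. SAP 4.4.3 is loose elsewhere too. For PFS and TTP it treats having no tumor assessment after baseline as the alternative to having a last evaluable one, as if every post-baseline assessment were evaluable. Its NPR and BOR categories contain no not-evaluable class. This stands as a point about intent, but it leaves the text ambiguous.

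A reader might infer three stronger things that the documents do not support:

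- **That missed scans inflate DOR.** Appendix 3 does say "When no imaging/measurement is done at all at a particular timepoint, the patient is not evaluable (NE) at that timepoint". But a scan that was not done has no assessment date, so it cannot set the censoring day. Only a performed but incomplete scan can.
- **That DOR is biased upward as a matter of course.** The curve moves only if a censored responder's last performed scan is not evaluable and another responder has an event in the added interval. Death remains a DOR event throughout. Appendix 3 also allows progression to be called from a partial scan, so the interval is not wholly unobserved.
- **That 37.5% against 50.0% is the expected size.** That contrast comes from one constructed cohort, between landmarks that the SAP reports.

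The not-evaluable text also sits in the modified RECIST appendix, whereas SAP DOR is based on RECIST v1.1. That weakens the link but does not remove it: the PFS and TTP rules, also RECIST v1.1, use the word *evaluable* and so presuppose the distinction.

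**Conclusion.** The inconsistency is real, appears in both documents and is resolved in neither. Its consequence is minor and conditional. An affected patient gains one scan interval, about 6 or 12 weeks. On average the 52-week Kaplan-Meier DOR rises by about 0.2 to 1.4 percentage points under assumed rates of not-evaluable scans between 5% and 30%, and by nothing if every responder's last scan is evaluable. The size rests on those assumed rates, exponential durations, the assumed follow-up patterns, and 4 to 8 responders per cohort. DOR is a descriptive secondary endpoint. The 18-week NPR and the Simon stopping and success rules do not use it and are unaffected. This is a clarification worth making, not a threat to the trial's conclusions.

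**What to change.** In SAP 4.4.3, censor DOR at the last *evaluable* tumor assessment, as for PFS and TTP. Align Protocol 3.4.1 and the synopsis at the next amendment. Protocol 9.6 requires amendments to be submitted to ethics committees and authorities, and this point alone does not justify one; until then the SAP can record the change as a clarification.

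No fallback date is needed. The scan that documented the response is itself evaluable, and the BOR rule in SAP 4.4.3 requires CR or PR at two consecutive visits at least 28 days apart.

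The cost is one word in the SAP, the same word later in the Protocol and synopsis, and slightly shorter censored DOR values for some patients. If the evaluable date was always intended, no result changes and the programming rule becomes unambiguous.

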The best overall response is determined once all the data for the patient are known.

The best overall response according to modified RECIST is interpreted as below:

3. **CR:** Complete disappearance of all tumor lesions (target and non-target) and no new measurable or unmeasurable lesions, confirmed by a consecutive assessment \geq 4 weeks from the date first documented. All lymph nodes short axes must be < 10 mm.
4. **PR:** Decrease in the sum of the diameters of all target and all new measurable lesions \geq 30% relative to baseline, in the absence of CR, confirmed by a consecutive assessment \geq 4 weeks from the date first documented.
5. **SD:** Criteria for CR, PR, and PD are not met.

Appendix 3

Modified Response Evaluation Criteria in Solid Tumors (cont.)

6. **PD:** Increase in the sum of the diameters of all target and all new measurable lesions $\geq 20\%$ relative to the nadir, which must be confirmed by a consecutive assessment ≥ 4 weeks from the date first documented as follows:

The confirmatory assessment shows an additional measurable increase in tumor burden as measured by the sum of the diameters of all target and all new measurable lesions.

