4.4.3 Secondary Efficacy Endpoints

Non progression rate (NPR) at 24 weeks is defined as the percentage of patients with “CR”, “CR (imputed)”, “PR”, “PR (imputed)”, “SD” or “SD (imputed)” at 24 weeks.

Week 24 occurs at Study Day 169. Allowing 20 days either side of the exact Week 24 study day, assessments that occur between Study Day 149 and Study Day 189 (inclusive) will be considered as a Week 24 assessment.

Individual patient response at 24 weeks, based on RECIST v1.1, will be categorized as “CR”, “CR (imputed)”, “PR”, “PR (imputed)”, “SD”, “SD (imputed)”, “PD”, “Death in absence of PD”, “Discontinuation in absence of PD” or “Missing” as follows:

1. any patient who recorded PD at any post-baseline tumor assessment up to Study Day 189 inclusive, will be classified as “PD”,
2. any remaining patient who died at or prior to Study Day 189 will be classified as “Death in the absence of PD”,
3. any remaining patient will be classified as “CR”, “PR”, or “SD” according to their Investigator-reported tumor assessment data that falls within the window of Study Day 149 – 189 inclusive (taking the worst case if there are two conflicting assessments within the window),
4. for a patient who does not meet any of the above criteria, but who has a nearby later assessment (up to Day 209), the patient will be classified as “CR (imputed)”, “PR (imputed)” or “SD (imputed)” according to the first tumor assessment in the extended window.

5. any remaining patient will be classified as "Discontinuation in absence of PD" if they have an End of Study date prior to Study Day 189 or, otherwise, as "Missing/Out of window".

Best overall response (BOR), based on RECIST v1.1, for an individual patient, is defined as the best overall response obtained until progressive disease, death or lost to follow up, whichever is the first, as follows:

1. CR for a patient with an overall tumour response assessment of CR at two consecutive visits at least 28 days apart. If applicable, any tumour assessment within the 28 day period must also record CR.
2. PR for a patient with an overall tumour response assessment of PR or CR at two consecutive visits at least 28 days apart without being a CR. If applicable, any tumour assessment within the 28 day period must also record PR or CR.
3. SD, for a patient with an overall tumour response assessment of SD, PR, or CR at one or more visits at least 42 days after start of study treatment, but are not a confirmed CR or PR.

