Modified best overall response (mBOR), based on modified RECIST, for an individual patient, is defined as the best overall response obtained until death or lost to follow up, whichever is the first. The mBOR categories are obtained in the same manner as for the BOR based on RECIST v1.1, as described above.

Modified best overall response will summarize the proportion of patients with each modified best overall response.

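### Modified best overall response reports a lone unconfirmed progression as PD, and lets a later SD outrank a confirmed one, contrary to Protocol Appendix 3

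*SAP*

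**What the plan says.** SAP 4.4.3 defines best overall response (BOR) and mBOR one after the other. BOR under RECIST v1.1 "is defined as the best overall response obtained until progressive disease, death or lost to follow up". For mBOR the window is longer: it "is defined as the best overall response obtained until death or lost to follow up, whichever is the first". The category rules are not restated: "The mBOR categories are obtained in the same manner as for the BOR based on RECIST v1.1".

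The rules carried over are, in order of rank:

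- CR or PR needs the response "at two consecutive visits at least 28 days apart".
- SD needs "SD, PR, or CR at one or more visits at least 42 days after start of study treatment", without a confirmed CR or PR.
- PD is given last: "PD, for a patient with an overall tumour response assessment of PD at any visit", if CR, PR and SD are not met.

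Protocol Appendix 3 sets the modified criteria. For best overall response, PD is a rise of at least 20% over the nadir "which must be confirmed by a consecutive assessment" at least 4 weeks later, and that assessment must show an additional measurable increase in tumor burden. SD is the residual class when CR, PR and PD are not met. The summary table at the start of Appendix 3 lists confirmation of progression as one of three differences from RECIST v1.1. Footnote 2 in SAP 2.1 refers to Appendix 3 as the governing definition. The SAP history for version 4.0 shows that BOR is the only modified-RECIST analysis now planned.

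**The concern.** The SAP carries a PD rule without confirmation into a table whose governing criteria require confirmation. A reader would take the PD row of that table as Appendix 3 PD, and for some patients it is not.

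The investigator's recorded data do not supply the missing step. Table 1 of Appendix 3 assigns PD at a single timepoint whenever the sum has risen by 20% or more; confirmation enters only at the best-overall-response level. That is the level the SAP derives, so the derivation has to apply it, and nothing else in the SAP does.

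The longer window adds a second departure. SD ranks above PD and mBOR does not stop at PD, so one SD visit after a confirmed PD turns the patient into SD. Such sequences can occur, because Protocol 3.1 and 4.6.2 allow treatment to continue after confirmed radiographic progression.

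At stake is the meaning of two rows in the only planned modified-RECIST output, each with an exact 95% confidence interval (SAP 4.4.4.1).

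**Working it through.** The plan states no figure for mBOR, so there is none to reproduce. The check applies both rule sets to the same visit sequences.

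**Inputs.** SAP 4.4.3: 28-day confirmation for CR and PR; SD from one visit at 42 days or later; PD from one record if nothing better is met; no cut-off at PD for mBOR. Appendix 3: confirmation of CR, PR and PD at 4 weeks or more; a further increase needed for PD; SD as the residual. Protocol Appendix 1: scans every 6 weeks (±5 days) for the first 24 weeks, so a first scan on day 38 is within schedule but too early to count as SD.

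| Timepoint responses | SAP mBOR | Appendix 3, read literally |
|---|---|---|
| PD at the only post-baseline scan | PD | SD |
| SD on day 38, then one PD, no later scan | PD | SD |
| PD, then SD at 42 days or later | SD | SD |
| SD at 42 days or later, then one PD | SD | SD |
| PD, then confirmed PR | PR | PR |
| PD twice, no other qualifying visit | PD | PD only if the second scan shows a further increase |
| PD confirmed, then SD | SD | PD |
| PD confirmed, then a single PR | SD | PD |
| SD at 42 days or later, then PD confirmed | SD | PD |

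**Reading the table.**

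1. Rows 1 and 2 are the first departure: one PD, no confirmation, no qualifying SD, PR or CR. The SAP says PD; the Appendix 3 condition for PD is not met.
2. Rows 3 to 5 show where there is no difference. An unconfirmed PD is not reported as PD if any visit at 42 days or later was SD, PR or CR.
3. In row 6 the SAP does not check for the further increase.
4. Rows 7 and 8 are the second departure, in the opposite direction: a confirmed PD is lost to a later visit.
5. Row 9 also differs on a literal reading, but it is not counted here. Crediting stability reached before progression is what a best-response summary normally does. The SAP need only say that it does so.
6. CR and PR use the same confirmation interval in both documents (28 days, 4 weeks), so their counts agree.

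**Size per patient.** In a cohort of 25, each affected patient changes the PD row by 1/25 = 4 percentage points. As an illustration with assumed counts, a PD row of 10/25 = 40% (exact 95% CI 21.1 to 61.3%) would become 6/25 = 24% (9.4 to 45.1%) if 4 patients were of the row 1 or row 2 type: 4 × 4 = 16 points. A patient of the row 7 or row 8 type would add 4 points to the PD row instead. The documents do not give the number of either type.

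**The case against.** The strongest reply is that the SAP has already adapted mBOR to the purpose of the modified criteria. Appendix 3 explains them by delayed responses that follow apparent progression. By dropping the cut-off at PD, the SAP lets a later response override an early PD, and the new-lesion and non-target rules come in through the modified timepoint response. This stands: the table is not RECIST v1.1 under another name, and what is missing is the confirmation step only.

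Second, Appendix 3 is not a complete algorithm. Read literally, it calls a patient SD when the only scan showed growth of 20% or more, and calling that patient PD is arguably the cautious choice. This also stands in part. A separate row for unconfirmed PD is not an Appendix 3 category either, so it must be declared as a choice. But caution does not explain the second departure, which works in the patient's favour.

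Third, SD after a confirmed PD is probably uncommon, because the sum must shrink back to less than 20% above the nadir. That is fair, and no frequency can be given.

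A reader might infer more than the documents support. One might take everyone whose last scan shows PD without a confirmatory scan, assume a share of 10 to 30%, and conclude that 2.5 to 7.5 of 25 patients are mislabelled. That counts the wrong group: anyone with SD, PR or CR at 42 days or later is SD under the SAP, and the share itself is not in the documents. One might also expect a clinical benefit rate to be distorted, but SAP 4.4.4.1 analyses CBR under RECIST v1.1 only.

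**Conclusion.** The point holds in a narrow form. The mBOR rule in SAP 4.4.3 contradicts the Appendix 3 criteria that the SAP cites, in two opposite directions, and no other text resolves it. The patients concerned are those with an unconfirmed PD and no qualifying SD, PR or CR, and those with SD, or a single unconfirmed response, after a confirmed PD. The effect is 4 percentage points per patient at n = 25 on the PD/SD split; the total is unknown.

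No decision depends on it. The Stage I and Stage II rules and the primary endpoint use NPR at 18 weeks under RECIST v1.1. This is a correction worth making for accurate labelling, of minor weight. The conclusion assumes that the mBOR program follows SAP 4.4.3 as written.

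**What to change.** In SAP 4.4.3, replace the cross-reference with a short mBOR rule of its own:

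- PD only when the next assessment, at least 4 weeks later, shows a further measurable increase in the sum that includes new measurable lesions.
- PD without a confirmatory scan shown in a separate row, *PD, unconfirmed*, with a note that Appendix 3 read literally would class these patients as SD and that the separate row is a deliberate choice.
- A second PD scan that does not show a further increase given a stated category.
- No SD credited from visits after a confirmed PD; SD reached before it is kept, and the text says so.

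The lesser alternative is one sentence stating that mBOR departs from Appendix 3 on confirmation of PD.

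The cost is a few lines of SAP text, the matching change in the derivation program and one extra table row. Appendix 3 already has the sum of diameters calculated at every assessment, so no new data are needed. The drawback is that an already small PD row becomes smaller by the number of patients moved out of it, and its confidence interval has to be read with that in mind.
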